Each trial is conducted as a pragmatic, multicentre, randomized (1:1), single-blinded, clinical trial. Participants are randomized to receive either 1) spinal anaesthesia (SA) or 2) general anaesthesia (GA). Study data is gathered continuously during admittance. Study personnel is blinded to the allocation of the patients, but clinical personnel and the patients are not blinded, as this is not feasible given the interventions.

RCT SAGA UKA is conducted as a pilot trial exclusively at Copenhagen University Hospital Hvidovre. RCT SAGA THA and RCT TKA are conducted as multicentre trials at both Copenhagen University Hospital Hvidovre and Lillebaelt Hospital – Vejle.

RANDOMIZATION

Permutated block-randomization (4 or 6), stratified by centre for RCT SAGA THA and TKA, with allocation disclosed using non-transparent envelopes. A designated person, at Clinical Orthopaedic Research Hvidovre, Copenhagen University Hospital Hvidovre, with no other relation to the project is responsible for generating randomization sequences and preparation of the envelopes. Included patients are randomised at least three days before their planned surgery date.

SAMPLE SIZE

v. 1.0

The primary endpoint of the study is whether patients are able to be safely mobilized during a 5meter walking test within 6 hours of surgery. In previous studies safe mobilization was achieved after GA for 95% of THA and TKA patients, while it was only achieved for 30-45% of THA and TKA patients after SA. For this study we decided on a minimal clinically relevant difference in proportions of 30%. To detect a clinically relevant difference between 60% achieving safe mobilization in one group and 90% of achieving safe mobilization in the other group within 6 hours, would require 32 patients in each arm of each trial (95% confidence, 80% power). We aim to include 37 participants to each arm of each trial, to allow for a 15% dropout-rate in each trial.

- RCT SAGA UKA: 74 participants (37 SA and 37 GA) all from Copenhagen University Hospital Hvidovre.
- RCT SAGA THA: 74 participants (37 SA and 37 GA) from Copenhagen University Hospital Hvidovre (intended nr. participants = 38) and Vejle Hospital (intended nr. participants = 36).
- RCT SAGA TKA: 74 participants (37 SA and 37 GA) from Copenhagen University Hospital Hvidovre (intended nr. participants = 38) and Vejle Hospital (intended nr. participants = 36).

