- Patients that after randomisation, but before being told their treatment allocation, withdrew consent to participate.
- Patients that after randomisation, but before receiving treatment, were found unsuited for inclusion based on inclusion and exclusion criteria or were not able to be operated in a standard setup in accordance with the SAGA protocol.

All patients are randomised at least 72 hours before surgery but are only informed of their treatment allocation in the operating room just before surgery. The research staff remains blinded. We do therefore not consider any of the above exclusions to be related to the treatment allocation, in line with recommendations regarding unbiased mITT analyses [1].

If patients withdrew their consent or declined surgery in the operating room after being told their allocation, they will be included in the mITT as a case with missing data in the primary endpoint, as we cannot consider this to be unrelated to the treatment allocation.

If cross over cases are present in the mITT population, a secondary per-protocol (PP) analysis will be conducted on the same population according to the actual treatment received. The mITT analysis will evaluate the postoperative recovery related to a setup with intended GA or SA, while a potential PP analysis will evaluate postoperative recovery based on receiving GA or SA. The mITT analysis will be the primary analysis of the studies.

TRIAL POPULATION

SCREENING DATA

Data on eligibility incl. age, sex and surgery type is collected and reported in aggregated form. This will function as a comparison between included and non-included patients. No statistical comparisons will be conducted.

ELIGIBILITY

Inclusion criteria:	Exclusion criteria:
 Clinical and radiological hip or knee osteoarthritis meeting the indications for primary THA, TKA or UKA 	• Lives in an institution
	 Uses walking aids, such as walker or a wheelchair.
• ≥18 years of age	• Terminal illness
 Able to speak and understand Danish 	 Has contraindications for either SA or GA
Able to give informed consent and must be cognitively intact	 Has objections to receiving either GA or SA
	 Requires anxiolytics as premedication prior to anaesthesia
	 Traumatic aetiology as a basis for surgical indication
	 Altered pain perception and / or neurologic affection due to diabetes or other disorders
	 Daily preoperative use of opioids > 30 mg of morphine milligram equivalents (MME)

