	 Standard primary arthroplasty procedure is evaluated not to be suitable
	 Women considered fertile but without sufficient birth control

RECRUITMENT, WITHDRAWAL AND FOLLOW-UP

Patients are pre-screened by the orthopaedic surgeons. At a standard preoperative physical examination 2-3 week prior to surgery, patients are asked whether research personnel can contact patients to provide them with study information. If patients consent to participation, the anaesthesiologist at the following standard preoperative anaesthesiologic examination will screen the patient for any contraindications for either SA or GA. Once screened by the anaesthesiologists, patients are considered included in the studies and baseline characteristics will be recorded.

Should the investigators become aware of previously unknown conditions, making included patients ineligible for participation, the investigators will withdraw the patient. These conditions include but are not limited to worsening of known disease, newly developed diseases or health conditions, and general safety concerns regarding anaesthesia.

In a CONSORT flow diagram the following will be reported; number of screened patients, number of excluded patients, number of randomized patients, number of patients allocated to each trial arm, number of patients that received anaesthesia in accordance with the allocation, and the number of patients that, after randomization, withdrew their consent, were excluded, or lost to follow-up.

BASELINE CHARACTERISTICS

The following baseline characteristics are registered at the time of inclusion:

Age, sex, height, weight, Charlson Comorbidity Index, Pain Catastrophizing Scale score, FRAILscale, ASA-score, preoperative blood sample results.

The baseline characteristics will be presented by intervention group using descriptive statistics. No statistical testing will be performed for baseline differences as suggested by the CONSORT-group [2].

ANALYSIS

OUTCOME DEFINITIONS

PRIMARY OUTCOME:

Ability to walk 5 meters 6 hours postoperatively:

Whether or not the participant is able to walk 5 meters safely and independently (also when using walking aid) within 6 hours of surgery evaluated by physiotherapists postoperatively.

Primary goal: Stable and safe 2-point gait with two crutches.

Secondary goal: Stable and safe 3-point gait with two crutches.

- Negative criteria:
 - Orthostatic: Dizziness, nausea, vomiting, fainting.

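### The third mITT exclusion stays open after the allocation is disclosed, so patients can be removed from the primary analysis with the arm known

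*SAP*

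**What the plan says.** ANALYSIS POPULATIONS makes the mITT the primary analysis and lists three exclusions after randomisation. The first (patient decides against surgery) and the second ("Patients that after randomisation, but before being told their treatment allocation, withdrew consent to participate") both end at disclosure. The third has two limbs: "Patients that after randomisation, but before receiving treatment, were found unsuited for inclusion based on inclusion and exclusion criteria", and patients who "were not able to be operated in a standard setup in accordance with the SAGA protocol". It ends only at the start of treatment.

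The same section says patients are "only informed of their treatment allocation in the operating room just before surgery" and that research staff stay blinded, and draws the conclusion: "We do therefore not consider any of the above exclusions to be related to the treatment allocation". Its next paragraph retains patients who withdraw consent or decline surgery after disclosure, as cases with a missing primary endpoint, "as we cannot consider this to be unrelated to the treatment allocation".

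Four other places bear on this:

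- TRIAL DESIGN states that "clinical personnel and the patients are not blinded".
- RECRUITMENT, WITHDRAWAL AND FOLLOW-UP gives an open-ended list of reasons for withdrawing an included patient, among them "general safety concerns regarding anaesthesia".
- MISSING DATA rules out both imputation and analysis of randomised patients who were excluded from the mITT.
- ANALYSIS METHODS describes the mITT as the patients who had the planned operation. Taken literally, that leaves out those who decline surgery after disclosure, whom ANALYSIS POPULATIONS keeps.

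**The concern.** Leaving randomised patients out of an mITT set is harmless only if the reason cannot depend on the arm. The SAP secures this for the first two exclusions by closing them at disclosure. The third stays open between disclosure and the start of treatment, when the people at the operating table know the arm. A finding in that interval that a patient is unsuited, or cannot be handled in the standard setup, can be influenced by which anaesthetic is about to be given.

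At stake is the comparability of the arms in the primary analysis of three small trials. A patient removed this way would be absent from the main result and from every missing-data analysis, so no planned analysis could show what the removal did. The text permits such exclusions; it does not show that they will happen.

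**Working it through.** **1. The wording, side by side**

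| Event | Window closes at | Treatment in the mITT |
|---|---|---|
| Patient decides against surgery | disclosure | excluded |
| Patient withdraws consent | disclosure | excluded |
| Found unsuited, or standard setup not possible | start of treatment | excluded |
| Withdrawal or refusal after disclosure | – | kept, endpoint missing |
| Other anaesthetic given than allocated | – | kept in allocated arm |

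Disclosure takes place in the operating room, before treatment. So there is an interval in which only the third exclusion still operates.

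**2. Does the SAP's justification reach that interval?** It gives two reasons: patients learn the allocation late, and research staff are blinded. The first says nothing about what follows disclosure. The second does not cover clinical personnel, who are unblinded. The SAP does not name who decides under the third exclusion.

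**3. Can the grounds depend on the arm?** The eligibility criteria include contraindications to, and objections to, either anaesthetic, and the withdrawal list includes anaesthetic safety concerns. A patient who objects on hearing the arm meets an exclusion criterion (removed) and may also count as declining (kept as missing). The SAP does not say which rule prevails.

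**4. Planning figures.** The point rests on no stated figure, but the planning size reproduces (two-sided 5%, 80% power, 60% against 90%, pooled variance, no continuity correction):

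n = [1.96·√(2·0.75·0.25) + 0.842·√(0.60·0.40 + 0.90·0.10)]² / 0.30² = 31.5, so 32 per arm. Then 32 × 1.15 = 36.8, so 37.

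**5. Effect of one patient.** GA is general and SA spinal anaesthesia; differences are GA minus SA, in percentage points. All counts are assumptions: 33/37 and 22/37 lie near the planning rates, and 35/37 with 11/37 to 17/37 lie near the earlier-study rates quoted under SAMPLE SIZE (95% and 30–45%).

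*Excluded but operated on, with an assessable walking test.* The largest possible shift in one arm is 1/37 = 2.7 points. From 33/37 − 22/37 = 29.73:

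| Patient removed | Calculation | Difference |
|---|---|---|
| SA failure | 33/37 − 22/36 | 28.08 |
| SA success | 33/37 − 21/36 | 30.86 |
| GA failure | 33/36 − 22/37 | 32.21 |
| GA success | 32/36 − 22/37 | 29.43 |

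Shifts in the same order at the earlier-study rates: from 35/37 − 11/37 = 64.86, −0.83, +1.95, +2.63 and −0.15; from 35/37 − 17/37 = 48.65, −1.28, +1.50, +2.63 and −0.15.

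For scale, the standard error at 33/37 and 22/37 is √(0.892·0.108/37 + 0.595·0.405/37) = 9.55 points.

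*Excluded and not operated on.* There is no walking result, so the available-data estimate is the same whether or not the patient is kept. Only the imputed analyses change. Under analysis 2 (missing GA counted as failure, missing SA as success):

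- GA case: 32/36 − 22/37 = 29.43 becomes 32/37 − 22/37 = 27.03, a shift of −2.40.
- SA case: 33/37 − 22/36 = 28.08 becomes 33/37 − 23/37 = 27.03, a shift of −1.05.

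**6. Several patients.** If k would-be failures leave one arm of 37, its success proportion rises by 37p/(37 − k) − p. For k = 1, 2, 3 this is 1.7, 3.4 and 5.3 points at p = 0.60, and 2.5, 5.1 and 7.9 points at p = 0.90.

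**The case against.** The strongest reply is that little is left open and blinded people guard it. RECRUITMENT, WITHDRAWAL AND FOLLOW-UP says investigators withdraw ineligible patients, and study personnel are blinded. Failure of the allocated technique is a cross-over and is analysed as allocated. Refusals after disclosure are kept. A contraindication to either anaesthetic makes a patient ineligible in both arms, so the criterion itself does not turn on allocation, and the anaesthesiologist screens for both before inclusion. The effect on the available-data estimate is zero for patients not operated on. The case with an assessable walking test further assumes that outcomes are collected after exclusion. The illustrated range straddles 30 points only because the assumed starting value is 29.7. The CONSORT flow and deviation reporting would make such cases visible.

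Much of this stands: the remaining interval is short, cases should be rare, and the likely effect is small. It does not close the gap. The SAP nowhere equates investigators with the blinded research staff, and unblinded clinicians could prompt a withdrawal in any case. A criterion that is symmetric on paper can still be detected unequally once the arm is known. The cross-over and refusal rules do not cover a finding of unsuitability or of a non-standard setup. Reporting a count does not return the patient to the analysis.

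**Conclusion.** The concern holds. For the interval between disclosure and treatment, the statement that no exclusion is related to allocation is unsupported, and it sits badly with the SAP's own rule for refusals in the same interval. This is a defect in a stated rule for the primary analysis set and should be fixed; it is not evidence of bias.

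The number and direction of such exclusions cannot be known from the document, and the effect is probably small. At the assumed counts, one assessable exclusion shifts the difference by between −1.7 points (28.08 − 29.73) and +2.6 points, against a standard error of about 9.6. One patient not operated on shifts the available-data estimate by 0 and analysis 2 by −2.4 (GA) or −1.1 (SA). A shift of this size could change the conclusion under the SAP's 30-point superiority rule only if the observed difference lay close to 30; at the earlier-study rates it would not.

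**What to change.** In ANALYSIS POPULATIONS, close the third exclusion at the moment the allocation is disclosed to the patient or to any clinician involved in the decision. Keep every later case in the mITT in its allocated arm, with the observed walking result if there is one and otherwise as a missing primary endpoint. State that this also governs a patient who objects to the anaesthetic after hearing the allocation.

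A documented decision by someone in the trial who is blinded to allocation would be an alternative, but a weaker one, because unblinded clinicians could still trigger the referral.

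As a minor companion edit, replace the short mITT definition in ANALYSIS METHODS with a reference to ANALYSIS POPULATIONS.

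The cost is two or three sentences of SAP text, with no new data, staff or visits and no change to the sample size. The downside is that a few more patients may carry a missing primary endpoint, which the planned missing-data analyses would then take into account.

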 - Motor control criteria: Poor muscle control or strength, insecure foot placement, impaired sensibility.

Stepwise mobilization course:

- Orthostatic test: from lying to sitting position.
- Motor control test: ability to move toes and lower limbs, firmly and securely planting the feet in the ground.
- Mobilization test: a few steps with a high walking frame.
- 5-Meter walking test using two crutches.

KEY SECONDARY OUTCOMES:

The key secondary outcomes are based on the first public registration of the study on https://euclinicaltrials.eu/ (2022-501221-21-00). Any erroneous disagreement between this first registration and the following registrations are corrected to coincide with the first registration.

Fulfilment of discharge criteria at 6 hours postoperatively:

v. 1.0

Fulfilment of functional discharge criteria is evaluated at both 4 and 6 hours postoperatively. This will be a dichotomous outcome where patients are either ready for discharge (fulfil all criteria) or are not ready for discharge (fail at least one criteria).

Pain levels at 4 and 6 hours postoperatively:

Pain levels (numerical relation scale (NRS) 0-10) during rest and activity (walking 5 meters) at 4 and 6 hours are registered through a nurse-assisted questionnaire.

Opioid use in Morphine Milligram Equivalents within the first 6 hours of surgery:

A cumulated amount of opioid in Morphine Milligram Equivalents within the first 6 hours postoperatively. Data on opioid use at the postoperative care unit and the bed ward is collected until 6 hours postoperatively.

Postoperative Nausea and Vomiting (PONV) at 4 and 6 hours postoperatively:

Nausea and vomiting levels (NRS 0-10) during rest and activity (walking 5 meters) at 4 and 6 hours are registered through a nurse-assisted questionnaire.

OTHER SECONDARY OUTCOMES:

Urinary retention: no spontaneous urination and bladder scan with >800 mL (>600 mL at Vejle) prior to discharge.

Vital signs: systolic and diastolic blood pressure, pulse, blood oxygen saturation, temperature. Postoperative blood sample results: Haemoglobin, serum-creatinine, and C-reactive protein. Opioid-Related Symptom Distress Scale – questionnaire (ORSDS): A score based on 20 opioid related symptoms evaluating the burden of these symptoms.

v. 1.0

Quality of Recovery – 15 score (QoR-15): a score based on 15 questions evaluating postoperative recovery.

3-minute Diagnostic Interview – Confusion Assessment Method (3D-CAM):

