Attitude towards anaesthesia type: Whether patients would like to receive similar anaesthesia for any following arthroplasty surgery.

Blood transfusions: Whether patients received blood transfusion.

Emergency room contacts, complications, readmission or mortality within 30 days of surgery.

ANALYSIS METHODS

The primary analysis aim is to assess whether the ability to be safely mobilized within 6 hours of hip and knee arthroplasty is different between the two anesthetic methods, GA and SA. The main hypothesis to be tested is that GA patients are more likely to be safely mobilized compared to SA patients within 6 hours of arthroplasty surgery. This will be assessed in the (mITT) population, defined as all patients having undergone the intended arthroplasty surgery, between the comparison groups (GA and SA) as allocated. Superiority of GA over SA in achieving safe mobilization within 6 hours of surgery will be claimed if a difference in proportions of 30% is found in favour of GA.

Main analysis of primary outcome: The proportion of patients able to be safely mobilized within 6 hours of surgery will be compared between intervention groups using a logistic regression model. A supporting model adjusted, including possible confounders such as age and sex, will also be conducted. Estimates from the analysis will be presented as odd-ratios and 95% confidence intervals, for both crude and adjusted models.

In case of cross-over cases, a per-protocol analysis with similar statistical methods will be conducted.

Key secondary continuous outcomes will be analysed using t-test or Wilcoxon rank-sum test depending on normality. Results from t-tests will be presented as differences in means and 95%

confidence interval. Results from Wilcoxon rank-sum tests will be presented as differences in medians and p-values. Key secondary dichotomous outcomes will be compared using fisher's exact test. A mixed-effect model accounting for repeated measures using patient ID as a random effect will be used to compare both 4 and 6 hours NRS scores for pain and PONV between the intervention groups.

Normality will be evaluated using quantile-quantile plots and histograms.

MISSING DATA

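### Preoperative opioid use up to 30 MME/day is allowed but neither tabulated at baseline nor used as a covariate for 6-hour opioid use and pain: a small, avoidable loss of precision and transparency

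*SAP*

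**What the plan says.** **Eligibility.** The exclusion criterion is "Daily preoperative use of opioids > 30 mg of morphine milligram equivalents (MME". Daily use from 0 up to and including 30 MME is therefore compatible with inclusion.

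**Baseline Characteristics.** The variables registered at inclusion are given as a closed list of nine: "Age, sex, height, weight, Charlson Comorbidity Index, Pain Catastrophizing Scale score, FRAILscale, ASA-score, preoperative blood sample results". They are to be shown by arm with descriptive statistics. Neither preoperative opioid use nor preoperative pain is listed.

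**Key Secondary Outcomes.** Opioid use is "A cumulated amount of opioid in Morphine Milligram Equivalents within the first 6 hours postoperatively", collected in the postoperative care unit and on the ward. Pain is scored on the NRS at 4 and 6 hours.

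**Analysis Methods.** The general rule is "Key secondary continuous outcomes will be analysed using t-test or Wilcoxon rank-sum test depending on normality". To compare the arms on pain and PONV, the SAP adds: "A mixed-effect model accounting for repeated measures using patient ID as a random effect will be used to compare both 4 and 6 hours NRS". No baseline covariate is named for either approach. The only adjusted model belongs to the primary outcome: "A supporting model adjusted, including possible confounders such as age and sex, will also be conducted".

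**Randomization.** "Permutated block-randomization (4 or 6), stratified by centre for RCT SAGA THA and TKA". Opioid use is not a stratification factor.

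**The concern.** The plan measures opioid consumption after surgery, and its eligibility rule treats consumption before surgery as relevant, but it neither displays nor uses the preoperative value. For 6-hour MME this is the most direct baseline variable available. The outcome definition also does not separate a patient's regular dose, if given in the window, from opioid given for postoperative pain.

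Two things are at stake. Variation due to habitual use stays in the error term, which widens the confidence interval. And each of the three trials is analysed alone with 37 per arm, so users may fall unevenly between arms by chance, and a reader of the baseline table could not see it.

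**Working it through.** **Arm size.** The SAP gives no figure on this point itself; the only input of its own is the arm size. The planning rates are "60% achieving safe mobilization in one group and 90% of achieving safe mobilization in the other group within 6 hours", with 95% confidence and 80% power. The two-sided pooled formula without continuity correction gives

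n = [1.96·√(2·0.75·0.25) + 0.8416·√(0.6·0.4 + 0.9·0.1)]² / 0.30² = (1.200 + 0.483)² / 0.09 ≈ 31.5, rounded up to 32.

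This matches the stated 32. Then 32 × 1.15 = 36.8, which gives the stated 37 per arm.

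**Assumptions.** The SAP gives no share of users and no SD for 6-hour MME. Assumed: 5%, 10% or 20% users; every user at 30 MME/day with even dosing; SD 10 MME apart from habitual use.

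**1. Habitual dose in the window.** 30 × 6/24 = 7.5 MME. This is the most that even dosing allows, since it puts every user at the limit.

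**2. Variance added.** p(1−p) × 7.5², relative to 10² = 100.

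| Users | Added variance | Share of 100 |
|---|---|---|
| 5% | 0.05 × 0.95 × 56.25 = 2.7 | 2.7% |
| 10% | 0.10 × 0.90 × 56.25 = 5.1 | 5.1% |
| 20% | 0.20 × 0.80 × 56.25 = 9.0 | 9.0% |

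**3. Chance imbalance.** Difference of two independent Binomial(37, p) counts:

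| Users | Arms differ by ≥3 users | Arms differ by ≥4 users |
|---|---|---|
| 5% | 0.173 | 0.061 |
| 10% | 0.327 | 0.171 |
| 20% | 0.466 | 0.307 |

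The chance that at least one of three trials differs by 4 or more is 1 − (1 − P)³, about 17%, 43% and 67%.

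**4. What an imbalance does to the estimate.** Three users: 3 × 7.5/37 = 0.61 MME. Four users: 4 × 7.5/37 = 0.81 MME. The standard error of the arm difference is 10 × √(2/37) = 2.3 MME, so these shifts are about 0.26 and 0.35 of one standard error.

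**5. Bias, error rate and power.** Simulation with 4,000 trials per setting, 37 per arm, residual SD 10, users 10-30%, 5 or 10 extra MME per user, and a true difference of 0 or 6 MME:

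| | Unadjusted t-test | Adjusted for user status |
|---|---|---|
| Type I error | 0.050-0.058 | 0.049-0.054 |
| Power | 0.65-0.72 | 0.71-0.73 |

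The mean unadjusted estimate lay within about 0.04 MME of the truth in every setting. Adjustment gained from about 0 to 8 points of power. The largest gain (0.646 to 0.722) came with 30% users at 10 extra MME, which is beyond the assumptions used in steps 1-4.

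No magnitude is worked out for pain, because nothing in the SAP links habitual dose to the NRS.

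**The case against.** A reader might infer that habitual use is mixed with, or confounds, the anaesthetic effect. The SAP does not support that. Allocation is randomised 1:1 and the main analysis is modified intention-to-treat as allocated, so habitual use has no systematic link to arm. The unadjusted confidence interval already allows for chance imbalance, and step 5 shows neither bias nor a materially raised error rate. An as-treated comparison would lack that protection, but the SAP describes its per-protocol analysis under the primary outcome, not for opioid use or pain.

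It can also be said that covariate choice for a secondary outcome is largely a matter of preference, and that the unadjusted comparison is valid. Both are true, and they limit the point to a minor one. They do not answer the missing baseline row: the SAP relies on descriptive display of the arms, which cannot work for a variable that is not listed.

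Further limits stand:
- Applying the criterion strictly needs only a yes or no at 30 MME. The SAP implies, but does not state, that a numeric dose is obtained.
- The SAP does not say whether regular opioids are given or counted in the 6-hour window.
- A case report form, not shown, may collect the dose. Even so, this SAP neither tabulates nor uses it.
- Pain is not left to a simple two-group test alone. A mixed model is planned, and the point is only that it names no opioid covariate.

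**Conclusion.** The point holds as a minor improvement in precision and reporting for two key secondary outcomes. It is not a flaw in the randomised comparison. Under the stated assumptions, habitual use adds about 3-9% to the variance of 6-hour MME, and a plausible chance imbalance shifts the estimate by roughly a quarter to a third of a standard error. With fewer users, or users below the limit, the effect is smaller. The user share, the even dosing and the SD are assumptions, not figures from the SAP. The primary outcome, the sample size and the main conclusion are untouched.

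**What to change.** 1. In Baseline Characteristics, add daily preoperative opioid use in MME/day, as established for the eligibility check, and show it by arm.
2. In Analysis Methods, prespecify that variable as a covariate in a linear model for cumulative 6-hour MME. State in advance that a robust or bootstrap confidence interval will be used if the data are skewed, and which of the two.
3. Add the same covariate to the mixed model already planned for pain NRS.
4. Report the unadjusted comparisons alongside.

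A covariate is preferable to a rank test stratified by user status. With 5% or 10% users, a trial of 74 has only about 4 (74 × 0.05 = 3.7) or 7 (74 × 0.10 = 7.4) users in both arms together, so the user stratum would be nearly empty.

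The cost is one extra field, recorded as a number rather than a yes or no, and one model term. If users turn out to be few, adjustment will change little, but the baseline table will at least show it.

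### The Pain Catastrophizing Scale score is recorded at inclusion but enters no pain analysis; naming it as a covariate in the planned pain mixed model would be a cheap, modest gain in precision

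*SAP*

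**What the plan says.** The Baseline Characteristics section lists what is registered at inclusion: "Age, sex, height, weight, Charlson Comorbidity Index, Pain Catastrophizing Scale score, FRAILscale, ASA-score, preoperative blood sample results". It then gives the use: "The baseline characteristics will be presented by intervention group using descriptive statistics". Baseline pain intensity and preoperative opioid dose are not in the list, so PCS is its only pain-related item.

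Pain at 4 and 6 hours and opioid use over the first 6 hours are key secondary outcomes. For these, Analysis Methods states: "Key secondary continuous outcomes will be analysed using t-test or Wilcoxon rank-sum test depending on normality". For pain and for nausea and vomiting scores at the two time points it adds: "A mixed-effect model accounting for repeated measures using patient ID as a random effect will be used". No fixed covariate is named there. Discharge readiness, the dichotomous key secondary outcome, goes to Fisher's exact test.

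The only covariate-adjusted analysis in the SAP belongs to the primary endpoint: "A supporting model adjusted, including possible confounders such as age and sex, will also be conducted".

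**The concern.** The SAP accepts covariate adjustment for the binary primary endpoint, as a supporting model. It does not carry the idea over to the continuous pain outcomes, where adjusting for a prognostic baseline variable narrows the interval directly. A pain-related candidate is already collected.

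Two things are at stake, both modest. The first is precision in trials of 32 to 37 patients per arm that were sized for a different endpoint. The second is pre-specification. The baseline table will show any chance imbalance in PCS, but the plan has no way to account for it, so an adjustment added once the table is seen would be post hoc.

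**Working it through.** **Inputs from the SAP.** 1:1 allocation; 60% against 90% for the primary endpoint; 95% confidence; 80% power; 32 evaluable and 37 recruited per arm of each trial; randomisation stratified by centre in THA and TKA. The SAP gives no SD, correlation or power for pain or opioid use.

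**The plan's own figure.** Two-sided 5%, pooled variance, no continuity correction:

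n = [1.96 × √(2 × 0.75 × 0.25) + 0.84 × √(0.6 × 0.4 + 0.9 × 0.1)]² / 0.3² = 31.5, so 32 per arm (power 80.6%). This reproduces. Then 32 × 1.15 = 36.8, so 37. These numbers concern mobilization; they set the sample available for pain but say nothing about power for it.

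**Formula for the gain.** With q covariates that explain a share R² of the within-arm variance, and N patients in total, the variance of the adjusted arm difference relative to the unadjusted one is about

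(1 − R²) × (N − 3) / (N − 3 − q).

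The second factor is the price of estimating the covariate effects. Interval width changes by the square root of the ratio. The formula is for one measurement per patient, so it is an approximation for a mixed model with two time points.

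**PCS alone, 32 per arm** (N = 64, q = 1, price 61/60 = 1.017). r is assumed. The smallest detectable difference at 80% power without adjustment is (1.96 + 0.84) × √(2/32) = 0.700 SD.

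| Assumed r | Variance ratio | Interval width | Detectable difference (SD) | Power where unadjusted power is 80% |
|---|---|---|---|---|
| 0 | 1.017 | +0.8% | – | – |
| 0.1 | 1.006 | +0.3% | 0.703 | 79.7% |
| 0.2 | 0.976 | −1.2% | 0.692 | 80.9% |
| 0.3 | 0.925 | −3.8% | 0.674 | 83.0% |
| 0.4 | 0.854 | −7.6% | 0.647 | 85.8% |

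Break-even is R² = 1/61 = 0.016, or r = 0.13. At 37 per arm it is 1/71 = 0.014, or r = 0.12.

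**PCS, age and sex together** (q = 3). Break-even R² is 3/71 = 4.2% at 37 per arm and 3/61 = 4.9% at 32 per arm. At 37 per arm the price is 71/68 = 1.044:

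- R² = 4%: 0.96 × 1.044 = 1.002, no gain.
- R² = 9%: 0.91 × 1.044 = 0.950, worth 1/0.950 − 1 = about 5% more patients.
- R² = 16%: 0.84 × 1.044 = 0.877, worth about 14% more patients.

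**All nine listed items, one term each, 32 per arm.** Break-even R² is 9/61 = 15%. At R² = 5% the interval is about 6% wider.

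**Size of a chance imbalance.** The 95% range for the difference in mean PCS between arms is ±1.96 × √(2/32) = ±0.49 SD. At r = 0.3 that corresponds to a shift of up to 0.3 × 0.49 = 0.15 SD in the unadjusted pain difference.

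**The case against.** The strongest reply is that nothing here is wrong. Under 1:1 randomisation the t-test, the Wilcoxon test and an unadjusted mixed model are all valid. Their intervals already allow for chance imbalance, and type I error is not inflated. Choosing unadjusted analyses for secondary outcomes that were not powered is defensible. All of this stands, and it is why the point is an improvement and not a correction.

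A reader might infer more than the SAP supports, in three ways.

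- That the pain and opioid comparisons are known to lose precision. The SAP calls no baseline item a predictor of pain or opioid use and gives no correlation. Below r of about 0.13, PCS gains nothing.
- That all the baseline items should be entered. In 64 to 74 patients that would lose precision unless they jointly explained roughly 13% (9/71) to 15% of the variance.
- That the gain is 1/(1 − R²) − 1, which gives 4.2%, 9.9% and 19.0% more patients at R² = 4%, 9% and 16%. This leaves out the price of the covariates. With three of them at 37 per arm the figures are about 0%, 5% and 14%.

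Two practical objections also stand. Opioid dose may be skewed, and the planned Wilcoxon test protects against that; a regression put in its place without a stated scale or robust method could be worse. And a complete-case adjusted model would drop patients with a missing PCS score, which could cancel a gain of this size.

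**Conclusion.** The point holds as a modest, low-risk improvement to the pain analysis. PCS is collected, it is the only pain-related baseline item, and no key secondary analysis uses it. For assumed correlations of 0.2 to 0.4, adjusting for it narrows the pain interval by about 1% to 8% at 32 per arm; the worst case is an interval about 1% wider. The case rests on PCS having at least a weak relation to early postoperative pain, which is an assumption. It does not rest on any flaw in the unadjusted tests. For opioid use the balance is less clear because of possible skewness, so adjustment there belongs in a supporting role.

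**What to change.** In Analysis Methods:

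- Name PCS score, as a continuous variable, as a fixed covariate in the existing mixed model for pain scores. In the THA and TKA trials also include centre, because it is the randomisation stratum. The UKA trial has one centre and needs PCS only.
- State that a missing PCS score does not remove a patient from the model, for example by simple imputation of the baseline mean.
- Report the unadjusted pain comparison alongside.
- For 6-hour opioid use keep the planned unadjusted test as the main result. Add a PCS-adjusted model, log-transformed or robust, as support; if a log scale is used, say how zero doses are handled.

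The cost is a few sentences, slightly more analysis work and one or two degrees of freedom. If PCS and centre together explained nothing, the variance ratio at 32 per arm would be 61/59 = 1.034, an interval about 1.7% wider. No new data and no new patients are needed. The wording should be fixed before outcome data are examined by arm.
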